1. LIST OF ABBREVIATIONS

Abbreviation	Definition
aDCT	annotated Data Collection Tool
CATI	Computer-Assisted Telephone Interviewing
CFR	Code of Federal Regulation
CIs	Confidence Intervals
DHPC	Direct Healthcare Professional Communication
EDC	Electronic Data Capture
IRB	Institutional Review Board
Lilly	Eli Lilly and Company
FDA	(US) Food and Drug Administration
HCPs	Healthcare Professionals
NIS	Non-Interventional Study
PBM	Pharmacy Benefits Manager
Pen	Multi-dose pen-injector device
SDLC	System Development Life Cycle
SERP	Safety Event Reporting Procedure
SOPs	Standard Operating Procedures
T2DM	Type 2 Diabetes Mellitus
UAT	User Acceptance Testing
UBC	United BioSource Corporation
US	United States
USPS	United States Postal Service

3. MILESTONES

Milestone	Planned date
Start of data collection	Estimated August 2016
End of data collection	Estimated November 2016

3.1. Rationale and Background

Diabetes, especially type 2 diabetes mellitus (T2DM), is increasing in global prevalence and associated economic and humanistic burdens. Despite tangible improvement in disease management, poor glycemic control remains a problem for individuals with diabetes (Inzucchi et al, 2012). Diabetes management guidelines recommend early initiation of insulin therapy in individuals with poor T2DM control or those with poor response to other anti-diabetes medications (Petznick A, 2011; ADA, 2014). In addition, insulin resistance and progressive loss of pancreatic beta-cell function are prodromal features of T2DM, which partially contribute to the need for high-dose insulin therapy—worldwide, about 30% of patients using basal insulin require more than 60 units daily (Gough et al, 2013), and approximately half of patients with T2DM will eventually require insulin to manage their diabetes (Jabbour, 2008).

Hypoglycemia is an identified risk of insulin therapy, and compared to other anti-diabetes medications, hypoglycemia risk is the highest with insulin (Maria Rotella et al, 2013). Hypoglycemia may occur due to low carbohydrate intake, alcohol consumption, exercise, or stress. On the other hand, failure to receive an adequate amount of insulin can result in hyperglycemia and poor diabetes control (Cornish, 2014). Hyperglycemia may occur due to excessive carbohydrate intake, less than planned exercise, illness or stress. Additionally, medication errors may contribute to these two conditions.

Insulin formulations are listed among the high-alert medications that have the potential to cause significant patient harm due to medication errors—in hospital setting, about 24% of insulin errors contributed to patient harm and 33% of deaths due to medication errors were attributed to insulin therapy (Cobaugh et al, 2013). Insulin medication errors occur across the continuum of medication-use process; however, prescribing and administration related medication errors are most common (Cobaugh et al, 2013). Medication errors involving insulin may include inadvertent interchange between insulin strengths or formulations, incorrect dosage, or incorrect use of pen-injector devices. These errors may result in hyper/hypoglycemia.

Humalog U-200 KwikPen is a prefilled and multi-dose pen-injector device (pen) that delivers insulin lispro by subcutaneous injection to improve glycemic control in adults and children with diabetes mellitus. Compared to Humalog U-100 KwikPen, it contains the same number of units of insulin lispro in half the volume. Despite warning messages on the pen and in the instructions for use, results from Human Factors studies performed in the United States (US) showed that a small percentage of patients may choose to withdraw insulin from the pen cartridge with a syringe if faced with device malfunction. Anecdotal information also indicates that patients may transfer insulin lispro from the pen cartridge into an insulin pump. Because of these data and to further optimize the benefit-risk balance of the presentation, additional Risk Minimization Measures beyond routine risk minimization measures (are being implemented, including communications to Healthcare Professionals (HCPs) and patients to minimize the risk of hyperglycemia and/or potentially hypoglycemia associated with insulin transfer from the pen cartridge to an alternative administration device without concentration adjustment and dose adjustment when transferring from Humalog U-100 KwikPen to Humalog U-200 KwikPen.

The additional Risk Minimization Measures will include a Direct Healthcare Professional Communication (DHPC) that will be distributed to pharmacists and prescribers (endocrinologists and mealtime insulin prescribing primary care physicians, nurse practitioners, and physician's

assistants). A patient communication document will be distributed in the single pen product sample packages that are routinely provided by HCPs to patients who have been newly prescribed Humalog U-200 KwikPen.

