5.4.1. Inclusion criteria

HCPs must meet the following criteria to be eligible for inclusion in the survey:

- HCPs are aware of the insulin product Humalog U-200 KwikPen; and
- HCPs are involved in the treatment and management of patients with diabetes.

Patients must meet all of the following criteria to be eligible for inclusion in the survey:

- Patients are 18 years or older;
- Patients have diabetes; and
- Patients have filled at least one (1) prescription of Humalog U-200 KwikPen within the past 90 days.

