- Self-reported practices with respect to communication of the key safety messages in clinical practice

Patients:

Screening questions:

- Agreement to participate
- Diagnosis of diabetes
- Filled a prescription for Humalog U-200 KwikPen within the past 90 days prior to survey launch
- 18 years or older
- Employment by Lilly, UBC, or the FDA

Data on demographic characteristics:

- Age
- Gender
- State
- Employment status
- Length of time with diabetes
- Length of time on any insulin therapy
- Length of time on Humalog U-200 KwikPen
- Length of time on mealtime Insulin used prior to Humalog U-200 KwikPen

Data pertaining to evaluation of the effectiveness of the risk minimization measures:

The survey includes questions/statements that will assess the risk understanding and behavior of patients. The understanding level and behaviors will be analyzed using descriptive statistics and CIs and will be used to determine the effectiveness of the risk minimization measures:

- Awareness of the Important Safety Information for Humalog U-200 KwikPen
- Receipt of or access to the Important Safety Information
- Understanding of the key safety messages
- Behavior with respect to the key safety messages

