 - More than 15 years
 - I don't know

5. Do you use injectable insulin to treat your diabetes?
- Yes
 - No **[GO TO Q10, TERMINATE AFTER Q14]**
 - I don't know **[GO TO Q10, TERMINATE AFTER Q14]**
 - I don't have diabetes **[GO TO Q10, TERMINATE AFTER Q14]**
6. For how long have you been using injectable insulin to manage your diabetes?
- Less than 1 year
 - 1 – 5 years
 - 6 – 10 years
 - 11 – 15 years
 - More than 15 years
 - I don't know **[GO TO Q10, TERMINATE AFTER Q14]**
7. Have you been prescribed Humalog® U-200 KwikPen® at least once?
- Yes
 - No **[GO TO Q10, TERMINATE AFTER Q14]**
 - I don't know **[GO TO Q10, TERMINATE AFTER Q14]**
 - I don't have diabetes/I don't use insulin **[GO TO Q10, TERMINATE AFTER Q14]**

8. For how long have you been using Humalog® U-200 KwikPen®?
- I have not used the Humalog® U-200 KwikPen® yet
 - Less than 3 months
 - 3 – 6 months
 - 7 – 12 months
 - More than 1 year
 - I don't know
 - I don't have diabetes/I don't use Humalog® U-200 KwikPen® **[GO TO Q10, TERMINATE AFTER Q14]**
9. What type of mealtime insulin did you use prior to using Humalog® U-200 KwikPen®?
- Humalog® U-100 KwikPen®
 - Other 100 Units/mL insulin
 - I don't know
 - I don't have diabetes/I don't use Humalog® U-200 KwikPen® **[TERMINATE AFTER Q14]**
10. What is your gender?
- Male
 - Female

11. What is the highest level of education you have completed?

- Less than high school
- Some high school
- High school graduate/GED (General Education Diploma)
- Some college/Associate's degree
- Bachelor's degree
- Master's degree
- Professional or Doctoral degree
- Prefer not to answer

12. In what state do you live?

[DROP-DOWN LIST INPUT WITH STATES TABLE, EXCLUDE PREFER NOT TO ANSWER]

13. Which of the following groups best describes your age?

- Under 18 **[TERMINATE AFTER Q14]**
- 18 – 29
- 30 – 39
- 40 – 49
- 50 – 59
- 60 – 69
- 70 or older
- Prefer not to answer **[TERMINATE AFTER Q14]**

14. Have you or any of your immediate family members ever worked for Eli Lilly and Company (Lilly), United BioSource Corporation (UBC), or the Food and Drug Administration (FDA)?
- Yes **[TERMINATE]**
 - No
 - I don't know **[TERMINATE]**

[END SCREENING QUESTIONS]

[BEGIN SURVEY CONTENT]

[BEGIN PREAMBLE 2 – DISPLAY ON SAME PAGE AS NEXT QUESTION]

The following questions are about Humalog® U-200 KwikPen®.

[END PREAMBLE 2]

15. Please answer True, False, or I don't know for each of the following statements about Humalog® U-200 KwikPen®.

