	[RANDOMIZE LIST]	True	False	I don't know
A	Humalog® U-200 KwikPen® should only be injected using the prefilled KwikPen device in which it is supplied.			
B	Your dose of insulin does not need to be converted when changing from one strength of Humalog to the other (for example, changing from Humalog U-100 KwikPen to Humalog® U-200 KwikPen®).			

16. Please answer Yes, No, or I don't know for each of the following statements about the Patient Information Letter/*IMPORTANT SAFETY INFORMATION FOR* Humalog® KwikPen®, 200 units/mL, U-200 *insulin lispro* injection.

[RANDOMIZE LIST]		Yes	No	I don't know
A	The first time I was prescribed Humalog® U-200 KwikPen®, my doctor or nurse provided me with a paper copy of the Patient Information Letter/ IMPORTANT SAFETY INFORMATION . (This letter was included with the patient sample pen pack.)			
B	My doctor or nurse offered to explain information about the safe use of Humalog® U-200 KwikPen® the first time I was prescribed this product.			
C	I think about the important safety information for Humalog® U-200 KwikPen® to remind myself of the risks when injecting my insulin.			
D	I should always have a backup pen with me.			
E	It is ok to transfer insulin from the pen using a syringe.			

17. Other than the information you have received from your doctor or nurse, from what sources have you received and/or accessed information on the safe use and understanding of the Humalog® U-200 KwikPen®. (Please select all that apply.)

[RANDOMIZE LIST – KEEP OTHER AT THE BOTTOM]

- Pharmacist
- Other Healthcare Professional
- Diabetes Support Group
- Internet
- Product Warning Label
- Other

[TELEPHONE: BEGIN SAFETY EVENT/PRODUCT COMPLAINT – KEEP ON ONE PAGE]

(INTERVIEWER: Please record if respondent spontaneously reported a safety event or product complaint during the course of this interview.)

- Yes
- No **[GO TO CLOSING 1]**

Enter Safety Event or Product Complaint Verbatim

[MULTILINE INPUT]

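### The patient screener ends the survey for anyone who does not report using *injectable* insulin, a condition absent from the stated eligibility, so some pump users of U-200 could be lost before the pen-only item

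*Protocol*

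**What the plan says.** **Rationale.** Section 3.1 reports syringe withdrawal seen in Human Factors studies and then adds: "Anecdotal information also indicates that patients may transfer insulin lispro from the pen cartridge into an insulin pump". It derives the measures from these data and describes the target risk as one "associated with insulin transfer from the pen cartridge to an alternative administration device without concentration adjustment". That wording is not limited to syringes.

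**Eligibility.** For product use, Section 5.4.1 asks only this: "Patients have filled at least one (1) prescription of Humalog U-200 KwikPen within the past 90 days". The other two patient criteria are age and diabetes. Neither Section 5.4.2 nor the patient screening list in Section 5.6 sets a condition on how insulin is delivered.

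**Screener.** Appendix I.3, question 5, asks "Do you use injectable insulin to treat your diabetes". The routing for the negative answer is "No [GO TO Q10, TERMINATE AFTER Q14", and *I don't know* is routed the same way. The term is not defined and there is no pump response. Question 6 repeats it: "For how long have you been using injectable insulin to manage your diabetes". Its *I don't know* answer also terminates.

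**Outcome items.** Item 15A says the product "should only be injected using the prefilled KwikPen device in which it is supplied". Item 16E concerns transfer with a syringe. Both come after question 14, where screened-out patients leave.

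**Terminology.** Section 5.6 lists the variable as "Length of time on any insulin therapy", and Section 5.5 is worded to the same effect. Section 5.9 reports the same variable with the word *injectable* added.

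**Analysis set.** Section 6.2 restricts the analysis to completed surveys.

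**The concern.** The screener adds an eligibility condition that the protocol body does not contain. The added condition may also be correlated with a behaviour the measures are meant to prevent. A patient who meets every criterion in Section 5.4.1, and who moves U-200 insulin into a pump, could answer no to question 5 in good faith and be recorded as ineligible.

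The restriction looks unintended. Question 7 offers a combined response for people without diabetes or not using insulin, which treats the preceding gate as a matter of insulin use, not route. Question 8 lets a patient who has not yet used the pen continue.

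What is at stake is the understanding rate for the pen-only message. If the patients lost know it less well than those kept, the rate is overstated. More respondents would not correct this, and the confidence interval does not reflect it. Section 4 intends to generalize from a representative population, which makes an unstated selection step worth removing.

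**Working it through.** **1. Path through the screener.** A patient with diabetes reaches question 5. *No* or *I don't know* sends the patient to question 10, then through to question 14, where the survey ends. Items 15A and 16E are never shown. Under Section 5.6.1 the respondent cannot go back, and under Section 5.11.1 the access code is inactivated after use, so a misreading cannot be repaired. Under Section 6.2 the patient is not analysed.

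**2. The protocol's own precision figures (Section 5.7, Table 1).** Half-width = 1.96 × √[p(1 − p)/280].
- At 90%: 1.96 × √(0.90 × 0.10/280) = 3.51 points; the protocol states 3.5.
- At 80%: 1.96 × √(0.80 × 0.20/280) = 4.69 points; the protocol states 4.7.

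The rows for 50%, 60% and 70% give 5.86, 5.74 and 5.37, matching the stated 5.9, 5.7 and 5.4. The table is correct and serves here only as a scale.

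**3. Size of the selection effect.** The documents give none of the inputs below; all are assumptions.
- f: share of U-200 fillers who use a pump, 1% to 5%.
- r: share of those screened out at question 5, 25% to 100%.
- p: correct rate on item 15A in other patients, 80% to 90%.
- q: correct rate in pump users, 0% to 40%.

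True rate = f·q + (1 − f)·p.

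Observed rate = [f(1 − r)·q + (1 − f)·p] / [f(1 − r) + (1 − f)].

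Worked case, f = 3%, r = 50%, p = 90%, q = 0: true = 0.97 × 0.90 = 87.3%; observed = 0.873/(0.015 + 0.97) = 0.873/0.985 = 88.6%; difference 1.3 points.

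| f | r | p | q | True % | Observed % | Difference (points) |
|---|---|---|---|---|---|---|
| 1% | 25% | 80% | 40% | 79.60 | 79.70 | 0.10 |
| 1% | 25% | 90% | 0% | 89.10 | 89.32 | 0.22 |
| 2% | 50% | 90% | 40% | 89.00 | 89.49 | 0.49 |
| 5% | 50% | 90% | 40% | 87.50 | 88.72 | 1.22 |
| 5% | 100% | 80% | 0% | 76.00 | 80.00 | 4.00 |
| 5% | 100% | 90% | 0% | 85.50 | 90.00 | 4.50 |

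Across shares of 1–5% the overstatement is about 0.1 to 4.5 points. Among the combinations calculated at 1%, 2% and 5%, only the last row exceeds the half-width at its observed rate (4.5 against 3.5). At an assumed share of 10% the range would be about 0.9 to 9.0 points. If pump users know the message as well as others (q = p), the bias is zero.

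**4. Could it change the conclusion?** Section 5.3 judges the measures by whether a majority of respondents are aware of the messages; I take this as more than 50%. In the most extreme case for shares up to 5% (f = 5%, r = 100%, q = 0), the true rate is 0.95 times the observed rate. It falls below 50% only if the observed rate is below 0.50/0.95 = 52.6%.

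**The case against.** The strongest reply is that the mechanism is conjecture. *Injectable* can describe the product as easily as the route, and the survey itself calls the product an insulin lispro injection. A pump user filling prescriptions for it may well answer yes. Section 5.9 uses *injectable* for the variable that Sections 5.5 and 5.6 describe without it, which suggests that the authors treated the terms as synonyms. This stands in part. It shows that no restriction by route was meant, but respondents see only the undefined word and a termination rule.

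The second reply is that pump transfer is not a patient key message. Section 4 gives patients a syringe message and names pumps only for healthcare professionals. Item 16E names a syringe, and no item records pump use. This stands fully and limits what any rewording can achieve.

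Two safeguards deserve mention. Section 5.9 reports ineligible patients with reasons, so a large count at question 5 would be visible, though not attributable to pumps. Section 5.1 describes user testing with 9 patients on the wording of selected questions, but does not say whether question 5 was among them.

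A reader might go further and infer that Section 3.1 sets injection against pump use, or that the survey is blind to the failure of greatest safety concern. The text supports neither. Section 3.1 describes the pen in one sentence and mentions pumps in a later, separate one, without saying that pump insulin is not injectable. It calls the pump evidence anecdotal and does not rank it above syringe withdrawal. Assuming that no pump user answers item 15A correctly is a worst case that equates behaviour with knowledge.

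**Conclusion.** The mismatch is a matter of text: question 5 imposes a condition found in neither the eligibility criteria nor the listed screening questions, and patients who fail it never reach the transfer items. The selection effect is a possibility, not a demonstrated bias. It requires some U-200 fillers to use a pump, some of those to read *injectable* as pen or syringe injection, and those lost to know the pen-only message less well than others. The documents give no data on any of the three.

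The size is therefore unknown. The illustrative range in the working is most likely within the survey's own precision and unlikely to change a conclusion that a majority understand. The case for acting is that the correction is free and restores the eligibility the protocol states. It does not rest on any showing that the result would be materially wrong.

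**What to change.** - Reword question 5 to *Do you use insulin (by pen, syringe or pump) to treat your diabetes?*
- Reword question 6 to ask how long the patient has been *using insulin*.
- Change the matching line in Section 5.9 to *any insulin therapy*, in line with Sections 5.5 and 5.6.

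Do not simply delete the termination at question 5. A patient who answers no would then meet question 6, which has no response for someone who does not inject and terminates on *I don't know*.

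The cost is the wording of two screening items and one line of the analysis section, with no added question and no extra respondents. The change keeps eligible pump users in the survey so that they can reach item 15A. It does not measure pump transfer in patients, because no patient item names a pump outside the reworded gate and none records pump use.

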4. RESEARCH QUESTIONS AND OBJECTIVES

The primary study objective is to evaluate the impact of the risk minimization measures on HCP and patient understanding regarding the risk of hypoglycemia and/or hyperglycemia due to medication errors associated with administration of Humalog U-200 KwikPen as communicated through the risk minimization measures.

The secondary objective is to evaluate behavior of HCPs and patients regarding the risk of hypoglycemia and/or hyperglycemia due to medication errors associated with administration of Humalog U-200 KwikPen as communicated through the risk minimization measures.

Specifically, this protocol refers to the surveys that are designed to assess the effectiveness of communications to HCPs and patients by assessing their understanding of the risks and safe use of Humalog U-200 KwikPen which were communicated through risk minimization measures including the following key safety messages:

HCPs:

- It is not necessary to adjust the insulin dose when switching from one strength of Humalog to the other
- Humalog U-200 KwikPen should not be transferred from the KwikPen to a syringe or insulin pump
- It is necessary to specify the Humalog strength on prescriptions
- It is necessary that patients always have a backup pen

Patients:

- It is not necessary to adjust the insulin dose when switching from one strength of Humalog to the other
- Humalog 200 units/mL should not be transferred from the KwikPen to a syringe as this could result in SEVERE OVERDOSE
- It is always necessary to carry a backup pen

The surveys are also designed to answer the following process research questions to assess the effectiveness of communications to HCPs and patients through the risk minimization measures. By testing a representative population about their knowledge and understanding of key safety message themes, we can generalize the:

HCPs:

- Extent of understanding of the key safety messages for Humalog U-200 KwikPen, as communicated through the DHPC (Were the key safety messages communicated in the DHPC understood by the HCP?)

- Extent of discussion between HCPs and patients when initially prescribing or dispensing Humalog U-200 KwikPen (Did the HCP convey the key safety messages in the label and DHPC to patients when they received their initial prescription of Humalog U-200 KwikPen?) with reference to the key safety messages.

Patients:

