5.4. Setting

The assessment surveys will be executed and the analysis will be completed within 18 months from product launch.

HCPs:

Eligible HCPs will receive an invitation letter ([APPENDIX I.2](#)) via email if an email address is available, or a letter via the United States Postal Service (USPS). The invitation letter will include: an overview of the rationale for the survey, information on how to access the survey online and by telephone, and a unique User Identification to ensure that the invitation is used only once. For telephone interviews, a trained interviewer, working from a computer-assisted telephone interviewing (CATI) script, will read questions or statements to the HCP. The letter will also contain a unique code that the respondent must provide when accessing the survey via the Internet or telephone. For telephone interviews, a trained interviewer, working from a computer-CATI script, will read questions or statements to the HCP. The average survey is expected to take approximately 15 minutes to complete.

A random sample of HCPs will be recruited to participate in the survey based on the list of HCPs to whom Lilly has provided a DHPC letter. The recruitment letter will indicate that participants will be compensated \$100 for their time and effort in completing the survey with the exception of HCPs who are licensed and practice in Minnesota, Vermont, Massachusetts or the District of Columbia in accordance with state laws. HCPs from these states can elect to participate however they will not be paid. Respondent-identifying information will be collected for the purposes of providing payment.

The response rate will be monitored throughout the data collection period. Reminder notices will be sent via email and or via the USPS. Additional recruitment methods may be explored during survey execution if necessary to achieve a total of 280 completed surveys.

Patients:

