[DROP DOWN LIST INPUT WITH STATES TABLE, EXCLUDE PREFER NOT TO ANSWER]

[IF RESPONDENT ANSWERS MASSACHUSETTS, MINNESOTA, VERMONT, OR DISTRICT OF COLUMBIA, DISPLAY REMINDER MESSAGE 1 ON SAME PAGE AND GO TO Q4.]

[REMINDER MESSAGE 1]: If you practice and you are licensed in the District of Columbia, Massachusetts, Minnesota, or Vermont just a reminder that we appreciate your participation; however, no compensation for your services will be provided in accordance with local laws.

4. Please choose an option about your participation in this survey.
 - i. ○ I will participate in the survey and provide my contact information.
 - ii. ○ I will participate in the survey but choose not to be paid.

5. Are you involved in the management of patients with diabetes? This includes prescribing medications to treat diabetes or providing education to help manage diabetes.
- Yes
 - No **[GO TO Q7, TERMINATE AFTER Q14]**
6. What is your role in the management of patients with diabetes?
- Physician
 - Nurse Practitioner
 - Physician Assistant
 - Registered Nurse **[GO TO Q8]**
 - Other **[GO TO Q8]**
7. What is your primary medical specialty?
- General Internal Medicine
 - Endocrinology/Diabetology
 - Family Medicine
 - Other
8. How many years have you been in practice as a physician, physician assistant, or nurse since completing your medical/nursing education?
- Less than 5 years
 - 5 – 10 years
 - 11 – 15 years
 - More than 15 years

9. In what type of facility do you work?
- General Practice
 - Hospital
 - Other
10. Are you aware of the insulin product Humalog® U-200 KwikPen®?
- Yes
 - No **[GO TO Q12, TERMINATE AFTER Q14]**
 - I don't know **[GO TO Q12, TERMINATE AFTER Q14]**
11. For how many patients have you prescribed, or managed their treatment with, Humalog® U-200 KwikPen®?
- 0 **[TERMINATE AFTER QUESTION 14 IF 140 OR MORE COMPLETE RESPONDENTS HAVE ANSWERED 0, WHERE 140 IS A CONFIGURABLE NUMBER]**
 - 1 – 5
 - 6 – 10
 - 11 – 20
 - More than 20

12. Have you or any of your immediate family members ever worked for Eli Lilly and Company (Lilly), United BioSource Corporation (UBC), or the Food and Drug Administration (FDA)?

- Yes **[TERMINATE AFTER QUESTION 14]**
- No
- I don't know **[TERMINATE AFTER QUESTION 14]**

13. Which of the following groups best describes your age?

- Less than 30
- 30 – 39
- 40 – 49
- 50 – 59
- 60 – 69
- 70 or older

14. What is your gender?

- Male
- Female

[END SCREENING QUESTIONS]

[BEGIN SURVEY CONTENT]

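### Pharmacists receive the DHPC and are not excluded from the HCP sample, but the HCP survey cannot identify them or report on discussion at dispensing.

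*Protocol*

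**What the plan says.** Section 3.1 (Rationale and Background) describes "a Direct Healthcare Professional Communication (DHPC) that will be distributed to pharmacists and prescribers". Its list of prescribers covers endocrinologists, primary care physicians, nurse practitioners and physician's assistants.

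Section 4 includes among the HCP research questions the "Extent of discussion between HCPs and patients when initially prescribing or dispensing Humalog U-200 KwikPen".

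Section 5.4 recruits a random sample of HCPs "based on the list of HCPs to whom Lilly has provided a DHPC letter", and section 5.6 names the same list as the data source. Sections 5.4.1 and 5.4.2 require awareness of the product and involvement in managing diabetes. They neither name nor exclude pharmacists.

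The HCP items in Appendix I.1 are:
- Q5, involvement in diabetes management: "This includes prescribing medications to treat diabetes or providing education to help manage diabetes".
- Q6, "What is your role in the management of patients with diabetes": physician, nurse practitioner, physician assistant, registered nurse or other. The last two skip the specialty item, Q7.
- Q8: "How many years have you been in practice as a physician, physician assistant, or nurse since completing your medical/nursing education".
- Q9, facility: general practice, hospital or other.
- Q11: "For how many patients have you prescribed, or managed their treatment with, Humalog® U-200 KwikPen". A zero answer ends the survey after Q14 once 140 completers (a configurable number) have answered 0.
- Q20 and Q21, on discussing safe use and the patient letter at initial prescription, are not displayed if Q11 is 0.

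**The concern.** Pharmacists are part of the intervention, are not removed from the sampling frame, and are implied by the research question. Section 5.11 also expects results to generalise to the HCPs educated about the product. The instrument has no place for them.

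Two results are at stake. The first is HCP behaviour: section 5.3 makes reported discussion with patients part of the effectiveness criterion, and the survey has no item that separates dispensing from prescribing. The second is knowledge: pharmacists' answers to Q15 enter the overall rate with no label, so a statement that the DHPC worked would cover a recipient group whose results nobody can see.

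An analysis plan cannot repair this. Section 5.6.1 does not let respondents return to an item and section 5.8 rules out queries, so what is not asked is not recoverable from the responses.

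**Working it through.** The point is about survey structure, so the main check is to follow a pharmacist through Appendix I.1.

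1. **Q5.** A pharmacist who neither manages nor educates answers No and is terminated after Q14, as the eligibility rule intends. One who educates patients can answer Yes and continue.
2. **Q6.** The only fitting answer is *Other*, which skips Q7. There is then no specialty value for the one HCP subgroup analysis that section 5.9 names.
3. **Q8.** The wording fits no pharmacist, yet section 5.11.1 requires an answer to every item presented.
4. **Q9.** In a retail pharmacy the answer is *Other*; in a hospital pharmacy it is *Hospital*. Neither identifies a pharmacist.
5. **Q11.** There are two branches:
   - *The item is read as not covering dispensing; answer 0.* Below the cap, the pharmacist completes, uses one of the 140 zero-answer places and is not shown Q20 and Q21. At the cap, the pharmacist is terminated after Q14.
   - *Managing treatment is read broadly; answer 1 or more.* Q20 and Q21 are shown, but both refer to the initial prescription, and the respondent is still recorded only as *Other*.

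In neither branch does any item record that the respondent is a pharmacist or dispenses.

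**Figures for scale.** Equation 1 in section 5.7 gives the half-width 1.96 × √(p(1 − p)/n). At n = 280 and p = 50%, 60%, 70%, 80% and 90% this is 5.86, 5.74, 5.37, 4.69 and 3.51 points, which reproduces Table 1 (5.9, 5.7, 5.4, 4.7, 3.5). Table 1 is not affected by this point.

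The protocol gives no pharmacist share, so the following shares are assumptions, applied to 280 completes with p = 80%:

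| Assumed share | Pharmacists (share × 280) | Half-width if they could be identified |
|---|---|---|
| 10% | 28 | 1.96 × √(0.16/28) = 14.8 points |
| 20% | 56 | 1.96 × √(0.16/56) = 10.5 points |
| 30% | 84 | 1.96 × √(0.16/84) = 8.6 points |

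A pharmacist estimate would be imprecise at these shares even with labels. Without labels it cannot be formed at all.

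**The case against.** The best defence is that this was always a survey of prescribers and nurses. Dispensing appears as a single word in section 4, and the explanation in the same bullet, like the endpoint in section 5.3, speaks only of a first prescription. Section 5.2 divides HCPs by whether they have prescribed, section 5.6 counts years in medicine or nursing, and the answer sheet is titled for prescribers. That may well be the intention. It does not settle the matter, because no text takes pharmacists out of the frame and section 4 still includes dispensing.

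A second defence is that the sponsor's list may hold profession, since section 5.9 counts invitations by specialty and each invitee has a unique code. This mitigates only in part: the protocol states no link from list to responses, and section 5.8 stores identifiers separately.

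Three stronger readings are tempting and are not supported:
- *That pharmacists will give practically no answers to Q20 and Q21.* The skip follows the answer at Q11, not the profession. Someone who passed Q5 because education counts as management may well answer 1 or more at Q11.
- *That counselling questions are hidden from eligible respondents who only hand over the product.* Those who neither manage nor educate leave at Q5 under the stated eligibility rule.
- *That losing registered nurses from the specialty analysis is part of the same defect.* They do skip Q7, but section 3.1 does not list them as DHPC recipients, so this is peripheral.

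**Conclusion.** The mismatch is real and should be corrected before the survey is programmed. As written, the survey responses cannot identify pharmacists, the dispensing part of the HCP research question cannot be reported, and any participating pharmacists' knowledge answers are pooled without a label. This follows from the item wording at any non-zero pharmacist share.

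How many respondents are affected is unknown. The range of 28 to 84 among 280 completes rests on an assumed 10% to 30% share of completers, after screening and any terminations over the cap; it is an illustration, not an estimate. How many pharmacists would miss Q20 and Q21 depends on how they read Q11, which the documents cannot tell us.

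**What to change.** Choose one of two courses and make the protocol consistent with it.

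- **Survey pharmacists.** Add a pharmacist option to Q6 and matching wording to Q8, a pharmacy setting to Q9, and dispensing to Q11, so that dispensers are shown Q20 and Q21. Adapt the wording of those two items to match. Report HCP results by role.
- **Do not survey pharmacists.** Exclude them explicitly from the sampling frame and in section 5.4.2, delete dispensing from the research question in section 4, and limit the conclusion to the HCP roles surveyed.

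The first course is a small instrument change, but it is not free. Section 5.1 reports user testing with 12 HCPs and section 6.3 reports IRB approval, so the reworded Q11, Q20 and Q21 would be untested core items and the IRB would need to be notified. The second course changes only the protocol text and the sample draw, at the price of saying nothing about pharmacists.
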